2. EXTERNAL IRB REVIEW HISTORY*

NA

This study has not been submitted to an external IRB.

3. PRIOR APPROVALS:

NA

4. OBJECTIVES*

This is a one-year study with a no-cost extension until 7.31.20. The objectives are:

1) To engage 26 socio-economically diverse subjects (2 cohorts of 13) with a current diagnosis of hypertension in beta testing an on-line mHealth platform (Our Whole Lives: an e-Health toolkit) that is being adapted to help manage and reduce high blood pressure and other cardiac risk factors by introducing mindfulness skills and lifestyle modification.

2) To identify barriers and facilitators of using OWL at home for self-monitoring and self-management of blood pressure and other cardiac risk factors. This is an 8-week pilot study that will assess the usability of a refined e-health platform for managing hypertension and other cardiac risk factors. There will be three in-person medical group visits to provide feedback on the refined system.

3) To redesign the OWL Orientation Session (OWL-O) by engaging 10 subjects from our existing OWL-H cohort(s) to quantitatively beta test and to complete a qualitative interview/focus group on an adapted version of the Orientation Session, based on their previous feedback.

5. BACKGROUND*

Nearly 80 million adults in the United States have high blood pressure. Few studies have specifically targeted minority populations with hypertension.^{1,2} Subject preferences, access to care, and socioeconomic/cultural determinants all add layers of complexity to this type of research. [name] developed and tested OWL for Chronic Pain (OWL CP) in subjects with chronic pain and chronic conditions with funding from the Patient Centered Outcomes Research Institute (2013-2017).³ OWL CP was also tested in a sample of 46 with funding from the Aetna Foundation.

Preliminary results from the Aetna foundation study showed a reduction in cardiac risk factors such as systolic blood pressure, stress, unhealthy eating, and sedentary behavior among subjects participating in the self-management program delivered by the OWL platform.⁴ OWL uses an innovative online community and self-management program to provide access to stress reduction, mind-body techniques, nutrition, exercise, and peer support. OWL provides educational materials including videos of clinician-led talks (stress reactivity, nutrition, movement, etc.). OWL also provides subjects a facilitated community blog, private journal, peer support, and an extensive resource library. OWL can be successfully accessed on a cell phone, tablet, or desktop.

INVESTIGATOR STUDY PLAN - REQUIRED

For this study, we refined the OWL CP platform to specifically address cardiac risk factors and hypertension, creating OWL for reducing Hypertension and Cardiac Risk Factors (OWL-H). Due to the proposed mixed methods, a transdisciplinary team reviewed quantitative and qualitative outcomes and will assist with refinement to the system. Based on preliminary findings and the availability of additional funding, we are taking the opportunity to make much-needed updates to the OWL-H website, particularly the Orientation Session, in order to increase the usability and user experience of the site. These changes will aid our team's long term plans of a large RCT to test the OWL-H platform's success in reducing hypertension and cardiac risk factors.

6. INCLUSION AND EXCLUSION CRITERIA*

We consented 25 subjects with self-reported high blood pressure. We collected baseline data on 24 subjects and 22 completed the protocol for the study (two participants were lost to follow-up and 1 withdrew). We will reach back out to those 22 subjects and plan to recruit 10 to complete beta testing and a qualitative interview/focus group on the updated Orientation Session. As these 10 participants will have already met the below listed criteria recently, and we are asking them to beta test the new Orientation Session only (and not collecting new data from the participants, we will not rescreen them.

Inclusion criteria:

1. Male and female subjects of all races and ethnicities who are English-speaking adults over the age of 18 and who have a current diagnosis of hypertension. OWL is currently only available in English.
2. Subjects' physical and mental health status will be sufficient to be able to comprehend instructions and participate in the interventions.
3. Subjects must be able to access computer technology (cellular phone, desktop, laptop) and the internet to utilize the online OWL-H platform.

Note: We will be videotaping the 3 cooking demonstrations (to take place during the group medical visits) to add this content to the OWL-H platform. This has been added to our fact sheets. We will ask patients to sign a release to allow us to film them during the cooking classes. If they choose not to consent to filming, they will still be able to take part in the class off camera.

Exclusion criteria with rationale:

1. Serious underlying systemic or co-morbid disease, including psychotic or manic symptoms, which preclude physical or cognitive ability to participate in the intervention. The risk-benefit ratio of the interventions for these individuals may be potentially higher than acceptable.
2. Active substance abuse, given that individuals who have active substance abuse pose a higher risk both to themselves and other members of the groups.
3. Beginning new hypertension treatments in the past week or planning to begin new hypertension treatments in the next few weeks or planning a major medical event in the next few weeks, which would interfere with accurately determining the effect of the intervention on impact in this study.

INVESTIGATOR STUDY PLAN - REQUIRED

4. Subjects who are pregnant or actively trying to become pregnant will be not included in this study given that the risk-benefit ratio of this intervention may be higher than acceptable for these individuals due to the potential onset of non-study related gestational diabetes and/or gestational hypertension. Determination of pregnancy status will be based upon subject self-report.
5. Subjects who are not willing to participate in the intervention or attend the group visits/interview/focus group.

7. STUDY-WIDE NUMBER OF SUBJECTS*

NA

8. STUDY-WIDE RECRUITMENT METHODS*

NA

9. STUDY TIMELINES*

This is a one-year open feasibility pilot study with an extension until July 2020. Planning and recruitment activities took place during months 1-3. In months 4-8, two cohorts participated in beta testing of the on-line OWL-H platform eight-week modules followed by a focus group convened at the end of the online component. During each cohort, we invited the subjects to 3 group visits to re-enforce the key content of OWL-H and answer questions on how to use the OWL system and get feedback about the system. During those visits, the subjects will also be invited to participate in three cooking classes that will be videotaped. These videos will be uploaded into the OWL-H system in months 9 to 12. Data analysis will be completed during months 9-12. Concurrently, during months 9-12, we will be re-enrolling 10 repeated subjects to beta test an updated version of the OWL-H Orientation Session. Once testing and data collection are complete, we will analyze and send our findings to BrightOutcome to make any final needed updates to the Orientation Session.

Time Line – one year

	Q1	Q2	Q3	Q4
IRB completed	X			
Revision and Addition of new content to OWL by Bright outcomes and [name]	X			
Beta Testing of OWL by Bright outcomes and [name]	X			
Recruitment		X	X	
Pilot testing of the new OWL-H		X	X	
Focus Group		X	X	
Revision of OWL-H				X
Preliminary Data Analysis				X
Re-Consent of 10 OWL-H Subjects				X
OWL-O Focus Groups/Interviews				X

INVESTIGATOR STUDY PLAN - REQUIRED

Full Data Analysis				X
Final Revision of OWL-H				X
Preparation of Grant Proposals				X
Publications				X

10. STUDY ENDPOINTS*

Our primary outcome is successful refinement of the OWL platform, based upon participant utilization and focus group feedback, to deliver information on self-management of hypertension and other cardiac risk factors, and to encourage self-monitoring of blood pressure.

Specific Aim 1 - To pilot test the OWL-H platform for 8 weeks with 26 patients with hypertension (2 cohorts) to refine its utility for home self-monitoring (number of times patients record home blood pressure and input this data onto OWL and engagement of self-management tools (i.e. # of logins, # of mind body sessions completed, # of times modules accessed each day)). Hypothesis 1: Eighty percent of patients will log in and record their blood pressures.

Specific Aim 2 - At the end of each cohort, conduct a focus group to obtain information about: 1) the barriers and facilitators of using the OWL platform and using OWL to self-monitor blood pressure at home, 2) satisfaction with OWL, 3) how OWL helped with reduction of number of cardiac risk factors (e.g., smoking, eating habits, perceived stress, and amount of exercise and health-related quality of life).

Specific Aim 3 – Using the previously collected feedback from the above aims, make key updates to the OWL Orientation Session. Re-consent 10 participants from the original OWL-H project to beta test and participate in a focus group/interview on the updated session, either on the UMMS campus or through a secure teleconference platform like Zoom. Implement changes as needed based on that feedback and testing.

11. PROCEDURES INVOLVED*

Recruitment

Primary OWL-H Project: Subjects were recruited from the Worcester area with a focus on the adult primary care clinics.

Subjects self-referred or were referred by their primary care provider. Subjects were contacted by the study RC via phone or e-mail to schedule a convenient time to complete the screening consent, review study objectives, and review eligibility criteria. An individual's name and contact information was kept separate from collected and stored data by utilizing a password protected spreadsheet on a school server and the OnCore patient and study tracking system. This information will be destroyed when feasible (the spreadsheet will be deleted immediately following completion of the study time period).

A HIPAA waiver was requested and approved to perform a medical record review to confirm eligibility, which was used to enroll the first 11 enrolled subjects in the study. The RC conducted a medical record review by querying the subject in EPIC by name and birthdate. The RC then

INVESTIGATOR STUDY PLAN - REQUIRED

confirmed that there was a high blood pressure medication listed on the medication chart and there was a diagnosis of hypertension on the problem list. With the current criteria not requiring a medication use, and self-reported instead of an official diagnosis of hypertension, a chart review is no longer required.

Once eligibility was determined, the study RC contacted the subject by phone or in-person to review the study fact sheet, obtain verbal consent for participation using that fact sheet, and to go over the HIPAA authorization and photo consent forms. The staff member who explained the study fact sheet and obtained verbal consent signed and dated the bottom of the fact sheet to provide confirmation of received consent. A copy of the study fact sheet, HIPAA authorization (for participation in group medical visits), and photo consent forms were provided to the subject prior to first group visit through the avenue of their choice (e.g., blank copies sent through email for their reference; hard copies mailed; or hard copies provided at individual in-person meeting). If possible, signed copies of the forms were collected prior to the first group visit. If not possible, they were collected during the check-in process at the first group visit. Before or during the first group visit, subjects were administered a baseline questionnaire (socio-demographic and general health information). Subjects were given the option of completing the questionnaire online (REDCap database) before the first group visit; in-person with a study staff member at an individual meeting or during the first group visit; or over the phone with a study staff member. No data was collected without completed consents from the subject.

OWL-O: The study RC will re-contact OWL-H participants that completed the entire protocol (i.e., were not lost to follow-up or withdrew) to make them aware of this project extension and ask whether they would like to participate in the updated orientation testing. Those that desire to will be consented with the OWL-O Beta Addendum Consent Fact Sheet. The study RC will sign and date the fact sheets to provide confirmation of consent.

OWL-H Orientation to Intervention (Week 1 – 8/21/19 and 10/30/19)

Eligible subjects were asked to participate in 3 in-person sessions. Participants had three options for data collection. They could fill out the baseline questionnaire online (REDCap) prior to the orientation, in-person with a study staff member prior to orientation, or during the first thirty minutes of the orientation. They also completed their photo consent and HIPAA authorization forms during that time, if it was not completed before this first group visit. Participants had baseline weight, height, waist circumference, pulse, and blood pressure readings completed at the orientation in a private room.

As part of this first group visit and cooking class session, a tutorial on how to use the OWL technology was demonstrated, participants were given their login information, and all participants were taught to take their blood pressures. As participants arrived, they were given the OWL-H Group Visit Check-In Form, which asked them basic questions about healthy lifestyle habits, any changes in medication, pain and mood rating, etc. This form was strictly for guiding the group leader (PI [name]) in her discussion with each patient individually, to track any potential AEs throughout the study, and to help guide the discussion. While this form collected data that assisted in the conduction of our research project (e.g., identifying potential AEs), any information identified as needing to be kept (again, solely the case for AEs

INVESTIGATOR STUDY PLAN - REQUIRED

or a note to file for a medication change (as the goal was for participants' meds to stay the same during the course of the study, though we in no way would ask them to go against their doctor's advice)) was recorded on a different form. This Group Visit Check-In Form was stored separately from any recorded data in a locked filing cabinet in a locked study staff member's office and was shredded after review by the PI and research staff (for potential mention of any AE or needed NTFs. If a potential AE was discovered using this form, the PI discussed it with the patient in private at each group visit, then completed the study adverse event log form (which, as previously approved by the IRB and in line with HRP-801, will guide the decision of when it needs to be reported to the IRB) if it was determined to be an adverse event.

Each participant received a blood pressure cuff and was asked to sign the Blood Pressure Cuff Return Agreement. All participants were observed taking their blood pressure prior to leaving the session with their cuff. Finally, we conducted and video recorded a cooking class on healthy food choices for reducing HTN during this time. Any subjects who did not consent to being video recorded were able to sit out of the scope of the camera during this presentation.

Mid-Session Feedback Group Visit (Week 4 – 9/11/19 and 11/20/19)

During week 4, subjects first filled out the OWL-H Group Visit Check-In Form, then completed the Midpoint Survey to answer questions about use of the OWL technology and to get feedback. They then participated in a short educational discussion regarding what they had learned so far using OWL. A second cooking demonstration took place during this session, which was video recorded, excluding on film anyone who did not consent to be video recorded. Any adverse events were recorded by the RC and PI.

Final Session (Week 8) and Focus Group (10/9/19 and 12/18/19)

During week 8, subjects again filled out the OWL-H Group Visit Check-In Form and participated in a group visit and cooking class to reinforce key content and provide certificates of completion. During this visit, a follow-up weight, height, waist circumference, and blood pressure were obtained and entered into REDCap. At the completion of the group visit, subjects were asked to complete a follow-up questionnaire, to return their blood pressure cuffs, and to participate in a one-hour focus group discussion with a facilitator who collected information about their experiences using OWL. If subjects did not come to the group, they were asked to come in to meet with the RC to obtain this data and return their cuff.

Updated OWL Orientation Testing and Feedback Session (Spring 2020)

Based on feedback collected from the OWL-H project surveys and focus groups (for both cohorts) and the availability of extra funding from our sponsor, we are making needed updates to the OWL-H Orientation Session to increase usability of the platform. Specifically, we plan to create tutorial videos that will be embedded in the session to familiarize participants with the various aspects of the OWL-H platform. We will also use this funding to create new Resource Section content (e.g., Healthy Shopping Guide, How to Eat Healthy When Eating Out, and lists of specific local resources for hypertension management), based on previous participant feedback.

INVESTIGATOR STUDY PLAN - REQUIRED

Ten subjects who previously consented to be part of the OWL-H project and completed the entire protocol will have the opportunity to take part in the quantitative beta testing and qualitative focus group/interview data collection for this updated Orientation Session. They will be asked to attend a research session, which will be held in a computer lab on the UMass campus or remotely by using a teleconference platform like Zoom, to complete a structured quantitative beta testing of the new session content. They will then be asked to participate in a semi-structured focus group/interview to collect qualitative feedback on the updated session. This research session should not last more than 2 hours.

OWL-H Platform

OWL is maintained on a HIPAA compliant server. All patients were given a username and password that was not linked to their real name or any health information. We will do the same for the OWL-O research session(s). At the orientation class for the OWL-H project, participants were given a blood pressure cuff for home use to monitor their blood pressure throughout the study. They were taught to use their blood pressure cuffs and were asked to measure and record blood pressure readings prior to logging into OWL.

The OWL platform is set up so that upon login a box appears to collect the participants daily blood pressure and pulse values, as well as information on their HTN medication use (if taking medication). For the OWL-O research session(s), participants will be given false values to enter in this daily reading box. The OWL-H intervention included watching a weekly 10-minute health topic video and interacting with a 15 to 20-minute meditation or body scan or gentle mindful movement at home. Additionally, there was a participant blog for participants to interact on. This was monitored daily by the research staff and [name]. For the OWL-O session(s), participants will be asked to only interact with the login screen, daily reading box, Orientation Session, and new education content.

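### The SAP lists no analysis of the blood pressure readings and logins recorded in OWL, so Hypothesis 1 (80% of patients) is left without an answer

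*Protocol*

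**What the plan says.** **Endpoint.** Protocol section 10, Specific Aim 1, measures home self-monitoring by the "number of times patients record home blood pressure and input this data onto OWL", and names the number of logins among its measures of engagement. Hypothesis 1 reads "Eighty percent of patients will log in and record their blood pressures". The section gives neither a denominator nor the number of readings that counts as recording.

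**Data capture.** Under OWL-H Platform in section 11, participants "were asked to measure and record blood pressure readings prior to logging into OWL", and "upon login a box appears to collect the participants daily blood pressure and pulse values". Section 13 lists the number of logins among the website data gathered.

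**Survey timing.** Section 11 lets participants complete the baseline questionnaire before orientation "or during the first thirty minutes of the orientation". At that visit "all participants were taught to take their blood pressures", and "Each participant received a blood pressure cuff and was asked to sign the Blood Pressure Cuff Return Agreement". At week 8: "At the completion of the group visit, subjects were asked to complete a follow-up questionnaire, to return their blood pressure cuffs".

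**SAP, Data Analysis.** Baseline and follow-up are compared by paired t-tests and descriptive statistics. Means and SDs are reported at both times for the BPKQ, the HTN-SCP-SE and items on self-monitoring of blood pressure. The usage paragraph covers three things: mind-body practices accessed, uses of the journal, and total time on OWL-H.

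**The concern.** The protocol sets one numeric target, and it concerns logging in and recording blood pressure. The SAP's usage paragraph contains neither component. A report that follows the SAP would therefore describe meditation, journal and time data, and would be silent on whether 80% of patients did what Hypothesis 1 says.

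The survey items would then be the only evidence on self-monitoring. They are a weaker substitute, because they compare two questionnaire occasions and cannot show whether recording was kept up between them. The pilot is meant to prepare a large randomised trial (section 5), which makes actual logging one of the most useful things it can report.

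**Working it through.** **1. Measure by measure.**

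| Measure | Named in Aim 1 or Hypothesis 1 | Collected | In the SAP |
|---|---|---|---|
| Readings entered in OWL | Yes | Yes (section 11) | No |
| Logins | Yes | Yes (section 13) | No |
| Proportion against 80% | Yes | Follows from the two above | No |
| Mind-body practices | Yes | Yes (section 13) | Yes |
| Journal use, total time | Not named | Yes | Yes |
| Self-monitoring survey items | Not named | Yes | Yes |

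**2. Which denominator.** Section 6 gives 25 consented, 24 with baseline data and 22 completed. Two were lost to follow-up and one withdrew: 25 − 2 − 1 = 22, which agrees. The smallest count that reaches 80% is:

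- 0.8 × 25 = 20.0, so 20
- 0.8 × 24 = 19.2, so 20
- 0.8 × 22 = 17.6, so 18

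The exact (Clopper-Pearson) 95% interval for r of n runs from the 0.025 quantile of Beta(r, n − r + 1) to the 0.975 quantile of Beta(r + 1, n − r). The documents give no observed count. For illustration, take r = 20 with all 20 among the completers:

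- 20/25 = 80.0% (59.3% to 93.2%)
- 20/24 = 83.3% (62.6% to 95.3%)
- 20/22 = 90.9% (70.8% to 98.9%)

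The choice can also reverse the answer. On the same assumption, 19 participants would be 19/22 = 86.4% but 19/25 = 76.0%.

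**3. Length of the recording period.** Orientation and final session were 8/21/19 and 10/9/19 for the first cohort, and 10/30/19 and 12/18/19 for the second. Each interval is 49 days, and 49 / 7 = 7 full weeks. Cuffs were due back at the final session, so an eighth weekly column would be nearly empty for attenders and could be misread as a drop in recording.

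**4. Entries that must not be counted.** Section 11 says OWL-O participants are given false values to type into the daily reading box. Section 14 says they keep the same study ID as in OWL-H. The SAP was submitted on 8/14/2020, after the OWL-O sessions planned for spring 2020. An export by study ID without date limits could therefore include invented readings.

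**5. What the survey change covers.** Teaching, cuff and request to measure all came at orientation, and baseline was planned before it or at its start. The order within that visit is not spelled out, so for the thirty-minute option baseline before cuff is a strong inference only. For participants who followed the sequence described for week 8, the follow-up questionnaire coincided with cuff return, so there is no later point.

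**The case against.** A reader might go further and infer that the survey comparison is invalid, or that any rise on the self-monitoring items was produced by the cuff. The documents do not support this, for four reasons:

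- The SAP does not credit the platform alone with any change. Cuff, teaching and group visits are part of the programme, and measuring before and after is what a single-group feasibility pilot does.
- The timing was not fixed for everyone. Section 27 let post-study data be given online or in person. Section 11 also describes baseline simply as before or during the first group visit, and sends those who missed week 8 to a separate meeting.
- The wording, format and recall period of the items are not given, so the size of any cuff effect cannot be calculated.
- The primary outcome rests on utilization and focus group feedback, which questionnaire timing does not touch.

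This answers the stronger reading. What remains of the timing issue is a reporting note.

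It can also be said that logged readings are no cleaner. Participants typed them in, they were obtained with the loaned cuff, and readings taken without a login are missed. All of that is true, but these are the readings that Aim 1 names.

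Finally, the SAP is a short account in the past tense, and the counts may have been produced without being listed. That is possible, but it does not put the analysis into the plan.

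**Conclusion.** The point stands as an omission from the SAP that should be corrected. Aim 1 names logged readings and logins, the protocol says both were collected, and the listed analyses include neither, so Hypothesis 1 has no analysis. No calculation in the documents is wrong, and nothing here shows that the 80% was or was not reached.

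The size of the denominator question is illustrative: the same 20 participants give 80%, 83% or 91%, with an exact interval on the 25 consented of 59% to 93%. This assumes that at least one logged reading is an acceptable meaning of recording, which section 10 does not define, and that the 20 are all completers. The survey timing is a minor matter of interpretation.

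**What to change.** Add to the SAP, from the existing platform data:

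1. The number and percentage of participants who logged in and entered at least one reading, with an exact 95% CI, set against the 80% in Hypothesis 1. Name one main denominator, for example the 25 consented, and show the 24 with baseline data and the 22 completers beside it.
2. Logins per participant, and the median (IQR) of readings per participant in each of the seven full weeks between orientation and final session.
3. An export rule that keeps only entries within each cohort's dates (8/21/19 to 10/9/19, and 10/30/19 to 12/18/19), so that OWL-O entries are excluded.
4. A short reporting note. The change in the self-monitoring items reflects platform, group visits, teaching and loaned cuff together. Where follow-up was completed at cuff return, the comparison has no later point. The logged readings do not isolate the platform either.

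The cost is one export, one table and a few sentences, with no new contact with participants. The remaining limitation is that readings taken without a login are not captured.
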